14.4 Clinical Laboratory Evaluation

A central laboratory will be used for protocol-specified clinical laboratory parameters. Laboratory parameters (chemistry, hematology, and urinalysis) will be summarized in conventional units using descriptive statistics at baseline and at each post-baseline time point. Changes from baseline will also be summarized for all continuous parameters. Summaries will be presented for change from methotrexate baseline (last assessment prior to the first dose of MTX in the MTX Run-in Period) and change from pegloticase baseline (last assessment prior to the first dose of pegloticase). The following laboratory parameters will be summarized:

- Hematology: hemoglobin, hematocrit, erythrocytes, leukocytes, neutrophils/leukocytes, lymphocytes/leukocytes, monocytes/leukocytes, eosinophils/leukocytes, basophils/leukocytes, platelets.
- Chemistry: albumin, aspartate aminotransferase, alanine aminotransferase, alkaline phosphatase, total bilirubin, creatinine, glucose, sodium, potassium, calcium, chloride, total protein, blood urea nitrogen, hs-CRP.
- Urinalysis: albumin:creatinine ratio.

If a continuous laboratory value is reported as either below or above the limits of quantification, the qualifiers will be dropped and the numeric value used in the analysis (e.g., “< 3” will be summarized as “3” and “> 200” will be summarized as “200”).

Shift tables for laboratory parameters by Common Terminology Criteria for Adverse Events (CTCAE) grade will be presented by visit for those laboratory parameters with CTCAE v5.0 grade defined.

A summary of subjects with elevated liver function tests (aspartate aminotransferase, alanine aminotransferase, alkaline phosphatase, and total bilirubin) and subjects who possibly meet Hy's law criteria will also be provided by visit and overall.

All laboratory tests will be listed, and results will be categorized as low, normal, or high based on their normal ranges. Separate listings of out-of-range results will also be presented.

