7.1.3 Methotrexate Overview and Risks

MTX is a folic acid reductase inhibitor used as a disease-modifying, anti-rheumatic drug for the treatment of autoimmune diseases. MTX is a drug well-known to rheumatologists, has a well-established and understood safety profile and is known to prevent the formation of anti-drug antibodies (Strand et al, 2017).

AEs that may be experienced by subjects treated with MTX include:

- Gastrointestinal: nausea, vomiting, diarrhea, stomatitis;
- Hematologic and oncologic: leukopenia, thrombocytopenia;
- Hepatic: hepatotoxicity, increased serum alkaline phosphatase, increased serum bilirubin, increased serum transaminases;
- Infection: increased susceptibility to infection; and
- General: malaise, fatigue, dizziness, alopecia, photosensitivity.

Additionally, MTX can cause fetal death or teratogenic effects. If either partner is receiving MTX, pregnancy should be avoided during therapy and for a minimum of 3 months after MTX therapy for the non-vasectomized male. For females of childbearing potential, pregnancy should be avoided for at least 1 ovulatory cycle after MTX therapy.

Baseline assessment will include a complete blood count with differential, hepatic enzymes, renal function tests and a chest x-ray.

MTX is available in both oral and injection formulations; however, subcutaneous (SC) administration may overcome some limitations of oral MTX therapy. In a trial of the PK profiles of MTX following oral and SC administration, the bioavailability of MTX was greater at all dose levels tested (10 mg, 15 mg, 20 mg, and 25 mg) for SC compared with oral administration, and a

dose-proportional increase in PK parameters was noted across all doses (Schiff and Sadowski 2017).

In addition, various clinical experiences suggest that SC MTX is more effective than oral MTX and may provide significant benefit even in patients in whom oral MTX proved to be inadequate. The increased efficacy of SC MTX resulting from higher drug exposure compared with oral MTX has been associated with a similar safety profile as oral MTX and in some reports even a lower frequency of gastrointestinal complaints (Vena et al, 2018). In a 6-month prospective, randomized, double-blind controlled trial of oral and SC MTX administration in 384 patients with active rheumatoid arthritis, SC administration was significantly more effective than oral administration at the same MTX dosage, with no difference in tolerability (Braun et al, 2008).

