7.3.2 Methotrexate Dose Selection

MTX is among the most well-studied agents shown to reduce anti-drug antibodies in numerous trials ([Strand et al, 2017](#)). MTX as monotherapy for rheumatoid arthritis and psoriatic arthritis is generally administered at doses of 7.5 to 15 mg/week, with doses titrated up as necessary and tolerated to 25 to 30 mg/week ([Visser and van der Heijde, 2009](#); [Ceponis and Kavanaugh, 2010](#); [Mouterde et al, 2011](#); [Mease 2013](#)). These dose levels have generally been both effective and safe. A similar dose range of MTX has been used in combination with biologic disease-modifying antirheumatic drugs when the biologic disease-modifying antirheumatic drugs have been used as therapy for both rheumatoid and psoriatic arthritis, as well as other conditions (REMICADE Product Labeling, 2020; HUMIRA Product Labeling, 2018; CIMZIA Product Labeling, 2019). As discussed in [Section 7.1.3](#), in the current trial, MTX will be administered SC, given its potential superior efficacy compared with oral administration.

A retrospective chart review of the effect of MTX and pegloticase in 10 uncontrolled gout patients provides support for the safety of the SC MTX with pegloticase regimen. Nine patients began SC MTX (25 mg weekly) prior to initiating pegloticase 8 mg every 2 weeks; the remaining patient began oral MTX (12.5 mg weekly) 14 days after the first pegloticase infusion. When MTX was administered with pegloticase, either as SC or oral formulation, the majority of patients (80%; 8/10) received at least 12 pegloticase infusions, were considered responders and no new safety concerns emerged ([Albert et al, 2019](#)).

The MTX dose in the current trial will be based on eGFR because renal excretion is the primary route of MTX elimination.

[Bressolle et al. \(1998\)](#) have shown that in rheumatoid arthritis patients, the half-life of MTX is doubled when creatinine clearance decreases to < 45 mL/min. The [RASUVO Full Prescribing Information](#) indicates that the dose of MTX should be reduced in patients who have renal

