Study Period	Visit	Target Day	Window for Reassignment to Scheduled Visit (days)
	Week 48	337	≥331

Table 2: Visit Windows for Assigning End of Study/ET and End of Pegloticase Visits to a Scheduled Visit (Hematology and Chemistry Laboratory Assessments, eGFR, urine albumin:creatinine ratio)

Study Period	Visit	Target Day	Window for Reassignment to Scheduled Visit (days)
Pegloticase + MTX	Day 1	1	1
	Week 2	15	2 – 29
	Week 6	43	30 – 71
	Week 14	99	72 – 134
	Week 24	169	135 – 211
	Week 36	253	212 - 295
	Week 48	337	≥296

Table 3: Visit Windows for Assigning End of Study/ET and End of Pegloticase Visits to a Scheduled Visit (hsCRP)

Study Period	Visit	Target Day	Window for Reassignment to Scheduled Visit (days)
Pegloticase + MTX	Day 1	1	1
	Week 14	99	2 – 134
	Week 24	169	135 – 211
	Week 36	253	212 – 295
	Week 48	337	≥296

Table 4: Visit Windows for Assigning End of Study/ET and End of Pegloticase Visits to a Scheduled Visit (DECT)

Study Period	Visit	Target Day	Window for Reassignment to Scheduled Visit (days)
Pegloticase + MTX	Day 1	1	1
	Week 14	99	2 – 134
	Week 24	169	135 – 253
	Week 48	337	≥254

Table 5: Visit Windows for Assigning ET and End of Pegloticase Visits to a Scheduled Visit (HAQ, CCI [REDACTED])

Study Period	Visit	Target Day	Window for Reassignment to Scheduled Visit (days)
Pegloticase + MTX	Day 1	1	1
	Week 6	43	2 – 71
	Week 14	99	72 – 120
	Week 20	141	121 – 155
	Week 24	169	156 – 211
	Week 36	253	212 – 295
	Week 48	337	≥296

Table 6: Visit Windows for Assigning ET and End of Pegloticase Visits to a Scheduled Visit (CCI [REDACTED], CCI [REDACTED])

Study Period	Visit	Target Day	Window for Reassignment to Scheduled Visit (days)
Pegloticase + MTX	Day 1	1	1

Study Period	Visit	Target Day	Window for Reassignment to Scheduled Visit (days)
	Week 14	99	2 – 134
	Week 24	169	135 – 211
	Week 36	253	212 – 295
	Week 48	337	≥296

Table 7: Visit Windows for Assigning ET and End of Pegloticase Visits to a Scheduled Visit
 (CCI [REDACTED], CCI [REDACTED])

Study Period	Visit	Target Day	Window for Reassignment to Scheduled Visit (days)
Pegloticase + MTX	Day 1	1	1
	Week 2	15	2 – 29
	Week 6	43	30 – 71
	Week 14	99	72 – 127
	Week 22	155	128 – 162
	Week 24	169	163 – 211
	Week 36	253	212 – 295
	Week 48	337	≥296

Table 8: Visit Windows for Assigning ET and End of Pegloticase Visits to a Scheduled Visit (sUA Assessments)

Study Period	Visit	Target Day	Window for Reassignment to Scheduled Visit (days)
Pegloticase + MTX	Day 1	1	1
	Week 2	15	2 – 22
	Week 4	29	23 – 36

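### SAP 14.4 summarizes white-cell differentials only as ratios to leukocytes and names no eGFR output, so the laboratory tables would not show low absolute counts that were not reported as AEs, or changes of eGFR category on MTX

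*SAP*

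**What the plan says.** SAP 14.4 introduces an explicit list of parameters to be summarized at each time point, with change from a methotrexate baseline and from a pegloticase baseline.

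- **Hematology.** The list opens "Hematology: hemoglobin, hematocrit, erythrocytes, leukocytes" and continues "neutrophils/leukocytes, lymphocytes/leukocytes, monocytes/leukocytes, eosinophils/leukocytes, basophils/leukocytes, platelets". No absolute count is named for any white-cell type.
- **Chemistry.** The list ends "alkaline phosphatase, total bilirubin, creatinine, glucose, sodium, potassium, calcium, chloride, total protein, blood urea nitrogen, hs-CRP". Creatinine is there and eGFR is not.
- **Grading.** Shift tables by CTCAE grade are planned "for those laboratory parameters with CTCAE v5.0 grade defined".
- **Listings.** "All laboratory tests will be listed, and results will be categorized as low, normal, or high based on their normal ranges", with separate listings of out-of-range results.

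Other places bear on this:

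- SAP section 7, Table 2, has analysis windows for "Hematology and Chemistry Laboratory Assessments, eGFR, urine albumin:creatinine ratio".
- Protocol 9.5.4.7 includes a differential leukocyte count and an MDRD-based eGFR among the safety laboratory tests. Protocol 9.6.7 says laboratory results will be summarized by visit and as change from Baseline.
- SAP section 15 declares no departure from the protocol's analyses.
- Protocol 7.1.3 gives "Hematologic and oncologic: leukopenia, thrombocytopenia" and greater susceptibility to infection as MTX risks.
- Protocol 7.3.2 states: "The MTX dose in the current trial will be based on eGFR because renal excretion is the primary" route of elimination. Protocol Table 9.2 has eGFR rows for 30 to <45 and for <30 mL/min/1.73 m2.

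**The concern.** The trial adds MTX to pegloticase, so the hematologic and renal laboratory tables are a main source on what the addition costs in safety. A ratio to leukocytes is not a count. Summaries of leukocytes and of the ratio, each on its own, do not show which subjects had a low absolute count. Creatinine does not map to an eGFR category without age, sex and race, yet eGFR is the quantity the protocol uses to set and adjust MTX.

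If 14.4 is programmed as written, two things are left to line-by-line reading of listings: low neutrophil or lymphocyte counts that no investigator reported as an AE, and movement between eGFR categories during MTX. The SAP windows eGFR in Table 2 but names no output for it in 14.4.

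**Working it through.** The plan gives no figure to reproduce. The check compares specified outputs with collected data and adds arithmetic. All subject values below are illustrative.

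**1. Do the leukocyte and ratio summaries together give the count?** Absolute count = leukocytes x ratio, within subject. Take two subjects with leukocytes 3.0 and 8.0 x 10^9/L and neutrophil ratios 0.30 and 0.60.

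- Pairing A: 3.0 x 0.30 = 0.9 and 8.0 x 0.60 = 4.8.
- Pairing B: 3.0 x 0.60 = 1.8 and 8.0 x 0.30 = 2.4.

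Both pairings have mean leukocytes (3.0 + 8.0)/2 = 5.5 and mean ratio (0.30 + 0.60)/2 = 0.45, with the same minimum, maximum and spread. The lowest count is 0.9 in one and 1.8 in the other. The planned tables would be identical.

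**2. How far can the count fall behind moderate changes?** Leukocytes go from 5.0 to 3.5 and the ratio from 0.50 to 0.30.

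- Leukocytes: (5.0 - 3.5)/5.0 = 30% fall.
- Neutrophil count: 5.0 x 0.50 = 2.5 and 3.5 x 0.30 = 1.05, so (2.5 - 1.05)/2.5 = 58% fall.

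A leukocyte value of 3.5 is not below 3.5, so it meets neither the run-in criterion nor a Table 9.2 row in protocol 9.4.6.3.2.2. Those criteria cover white cells, platelets and hematocrit and have no neutrophil or lymphocyte item.

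**3. Can creatinine stand in for eGFR?** Protocol 9.5.4.7 gives eGFR = 175 x creatinine^-1.154 x age^-0.203 x 0.742 (if female) x 1.212 (if African American). At 1.8 mg/dL, 175 x 1.8^-1.154 = 88.8.

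| Subject | Calculation | eGFR | Category |
|---|---|---|---|
| Woman, 75, not African American | 88.8 x 75^-0.203 x 0.742 | 27.4 | <30 |
| Man, 60, not African American | 88.8 x 60^-0.203 | 38.7 | 30 to <45 |
| African American man, 40 | 88.8 x 40^-0.203 x 1.212 | 50.9 | >=45 |

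Solving the same equation for creatinine at ages 40, 60 and 75, for both sexes and both race terms, eGFR 45 corresponds to 1.17-2.00 mg/dL and eGFR 30 to 1.67-2.85 mg/dL. Between 1.67 and 2.00 mg/dL a subject could be in any of the three categories.

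**4. Do other planned outputs fill the gap?**

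- *AE tables (SAP 14.2).* Protocol 9.5.4.1.3 grades AEs, abnormal laboratory values included, and the SAP tabulates maximum grade. Under protocol 9.5.4.1.1.1, a laboratory finding that the investigator does not judge a clinically significant change is not an AE.
- *Listings (SAP 14.4).* They show individual values and range flags, but no incidence, grade or shift.
- *MTX dose reductions (SAP 14.1).* Laboratory, AE and titration reasons are pooled, and only subjects whose dose was reduced are counted.
- *Deviations (SAP 9.2).* Incorrect dosing is one example of a major deviation, but it is not split by eGFR.

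**The case against.** The strongest reply is that little can stay hidden. The count is the product of two factors, and 14.4 summarizes both from two baselines. If one stays flat, the other must move: a neutrophil fraction dropping from 60% to 20% at steady leukocytes would show in the ratio line. With about 30 subjects, the flagged listings can be read in full. The protocol's MTX hematology criteria use white cells, platelets and hematocrit, and all three are summarized. Protocol 9.5.4.7 places eGFR inside the creatinine item and Table 2 windows it, so its absence from the 14.4 list may be a drafting slip. The table index in Appendix C, which might settle that, is redacted in the public copy.

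Most of this stands, and it limits the point. It does not cover moderate falls in both factors (step 2), the loss of within-subject pairing (step 1), or eGFR category (step 3).

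A reader might also infer more than the documents support:

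- *That neutropenia or lymphopenia is never graded.* Cytopenias judged clinically significant are graded and tabulated as AEs.
- *That ratios cannot enter the shift tables.* That depends on CTCAE v5.0 criteria, which neither document reproduces.
- *That the SAP ignores eGFR.* It is missing from the 14.4 list, not from Table 2.
- *That MTX treatment below renal limits goes uncounted.* Subjects at 30 to <45 are eligible and dosed by design, so a raw count below 45 is not a count of treatment outside a limit. For <30 on treatment, Table 9.2 gives dose guidance that includes continued MTX as an option.

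**Conclusion.** The point holds as a gap in the specified laboratory outputs. SAP 14.4 names no absolute neutrophil or lymphocyte count, no eGFR summary and no eGFR category shift, and no other specified output supplies them. The gap covers low absolute counts not reported as AEs, and the number of subjects who changed eGFR category on MTX, with the dose they were taking.

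Its size in subjects cannot be given, because the documents contain no rates for either event. The arithmetic shows only that the planned tables can be the same for materially different counts, and that a single creatinine value can span all three eGFR categories. The conclusion assumes that 14.4 is programmed as worded and that the redacted table index adds nothing. The primary analysis, sample size and error rates are unaffected.

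**What to change.** Amend SAP 14.4 before database lock, since SAP section 6 treats later analyses as post hoc:

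1. Add absolute neutrophil and lymphocyte counts, as reported or derived as leukocytes x ratio, to the summaries. Include them in the shift tables where CTCAE v5.0 defines a grade.
2. Add eGFR summaries by visit, using the Table 2 windows. Add a shift table from both the methotrexate and the pegloticase baseline across the protocol's own categories (>=45, 30 to <45, <30 mL/min/1.73 m2), shown alongside the MTX dose taken. A shift table keeps subjects enrolled at 30 to <45 from being counted as events.
3. Reconcile the 14.4 list with SAP Table 2 and protocol 9.5.4.7.

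The source data are already collected. The cost is SAP wording, two derived counts where they are not reported directly, and a few extra safety tables. No dose or clinical rule is proposed.

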14.5 Vital Signs

Vital signs (including heart rate, respiratory rate, systolic blood pressure, diastolic blood pressure, and temperature), weight and BMI will be summarized using descriptive statistics at baseline and at each applicable post-baseline time point. Changes from baseline will also be summarized. During the Pegloticase + MTX Treatment period, vitals will be measured pre-infusion and post-infusion. Weight will only be measured at Screening, pre-infusion on Day 1, pre-infusion at Week 24, at the non-infusion end of pegloticase infusions visit (if applicable) and at Week 24 or 48/End of Trial/Early Termination Visits.

14.6 Physical Examination

Physical examination results will be listed for each subject.

14.7 Electrocardiogram

An electrocardiogram (ECG) will be performed at Screening for all subjects and at the discretion of the investigator thereafter. The results will be recorded as normal or abnormal on the eCRF and all abnormal results will be evaluated as clinically significant (CS) or not clinically significant (NCS) by the investigator. A summary of ECG results at Screening and a summary of any post-Screening results will be presented. All ECG results will be listed.

15. CHANGES TO PROTOCOL-SPECIFIED ANALYSES

There are no changes to the protocol-specified analyses.

17. APPENDICES

APPENDIX A: PRESENTATION OF DATA AND PROGRAMMING SPECIFICATIONS

Scoring for the CCI

For each of the [] sections of the CCI

[REDACTED]

[REDACTED]

[REDACTED]

The aids and devices are assigned to the individual sections as follows:

- CCI - [REDACTED]
- [REDACTED] - [REDACTED]

CCI

[REDACTED]

[REDACTED]

[REDACTED]

Missing or incomplete dates

Medications

For prior and concomitant medications with incomplete dates, the following rules will be used to impute start and/or stop dates for the purposes of determining if a medication is prior, concomitant in the MTX Run-in Period, or concomitant in the Pegloticase + MTX Period. Imputed dates will not be presented in the data listings.

For partial start dates:

- If the month and year are provided and day is missing, and the month and year match the month and the year of the first pegloticase dose date AND match the month and the year of the first MTX dose (i.e. the MTX and pegloticase started in the same month), the day of the first dose date of MTX will be imputed. Otherwise, if the month and year match the

month and year of the first pegloticase dose date, then the first dose date of pegloticase will be imputed. Otherwise, if the month and year match the month and year of the first MTX dose date, then the first dose date of MTX will be imputed. Otherwise, the first of the month will be used.

- If the year is provided and the month and day are missing and the year matches the year of the first pegloticase dose date and the year matches the year of the first MTX dose date, the month and day of the first MTX date will be imputed. Otherwise, if the year matches the year of the first dose of pegloticase, the first dose date of pegloticase will be imputed. Otherwise, if the year matches the year of the first MTX date, then the first dose date of MTX will be imputed. Otherwise, January will be used.
- If the start date is completely missing, the start date will not be imputed. If the stop date is after first dose date of pegloticase, the medication will be considered to be both prior, concomitant in the MTX Run-in Period, and concomitant in the Pegloticase + MTX Period. If the stop date is after the first dose date of MTX, but prior to the first dose date of pegloticase, the medication will be considered to be prior and concomitant in the MTX Run-in Period. If the stop date is prior to the first dose date of MTX, the medication will be considered to be prior only.
- If the stop date is complete and the imputed start date is after the actual stop date, then the start date will be imputed as the stop date.

For partial stop dates:

- If the month and year of stop are provided, but the day is missing, then the last day of the month will be used.
- If the year of stop is provided, but the month and day are missing, then December 31st of that year will be used.
- If the stop date is completely missing, then the date of last study visit will be used.

Adverse Events

For adverse events with incomplete dates, the following rules will be used to impute start and/or stop dates for the sole purpose of determining if an AE is treatment-emergent in the MTX Run-in Period or Pegloticase + MTX Period. Imputed dates will not appear in the data listings.

For partial start dates:

- If the month and year of adverse event onset are provided but day is missing
 - If the month and year match the month and year of the first dose of MTX in the MTX Run-in Period AND match the month and year of the first infusion of pegloticase in the Pegloticase + MTX Period, the first dose date of MTX in the

Run-in Period will be imputed and the event will be considered treatment emergent in the MTX Run-in Period and Pegloticase + MTX Period.

- Otherwise, if the month and year match the month and the year of the first dose date of pegloticase, the day of the first infusion date of pegloticase will be imputed and the AE will be considered treatment-emergent in the Pegloticase + MTX Period.
- Otherwise, if the month and year match the month and the year of the first dose date of MTX, the day of the first dose date of MTX will be imputed and the AE will be considered treatment-emergent in the MTX Run-in Period.
- Otherwise, the first of the month will be used and the treatment-emergent status will be assessed relative to the first infusion date of pegloticase and the first dose date of MTX.
- If the year of adverse event onset is provided, but the month and day are missing
 - If the year matches the year of the first dose of MTX in the MTX Run-in Period AND matches the year of the first infusion of pegloticase in the Pegloticase + MTX Period, the first dose date of MTX in the Run-in Period will be imputed and the event will be considered treatment emergent in the MTX Run-in Period and Pegloticase + MTX Period.
 - Otherwise, If the year matches the year of the first infusion date of pegloticase, the month and the day of the first infusion date of pegloticase will be imputed, and the AE will be considered treatment-emergent in the Pegloticase + MTX Period.
 - Otherwise, if the year matches the year of the first dose date of MTX, the month and day of the first dose of MTX will be imputed and the AE will be considered treatment-emergent in the MTX Run-in Period.
 - Otherwise, January 1st will be used and the treatment-emergent status will be assessed relative to the dosing start date of pegloticase and the first dose date of MTX.
- If the start date is completely missing, the AE will be considered treatment-emergent in the Pegloticase + MTX Period and the MTX Run-in Period, unless the stop date is complete or provides enough partial information to rule out a treatment-emergent status in the Treatment Period. This should be a rare occurrence.

If the stop date is complete and the imputed start date is after the actual stop date, then the start date will be imputed as the stop date.

Gout History

If date of first gout attack or date of first gout diagnosis are incomplete, impute as follows for calculating time since first gout attack and time since first gout diagnosis:

- If day is missing, impute as first day of month.
- If day and month are missing, impute as January 1 of the year.
- If year is missing, do not impute and time since date will be missing.

Standard Calculations

Variables requiring calculation will be derived using the following formulas:

- **Days** – A duration expressed in days between 1 date (date1) and another later date (date2) is calculated using the formulas noted below:
duration in days = date2 – date1 + 1
- **Age** – Age will be calculated as (informed consent date - date of birth + 1) / 365.25 and truncated to complete years. If the date of birth is only partially available, the first of the month will be imputed for any missing days and January will be imputed for any missing months.
- **Height** – Height entries made in inches (in) are converted to centimeters (cm) using the following formula:
height (cm) = height (in) × 2.54.
- **Weight** – Weight entries made in pounds (lb) are converted to kilograms (kg) using the following formula:
weight (kg) = weight (lb)/2.2046.
- **Temperature** – Temperature entries in degrees Fahrenheit are converted to degrees centigrade using the following formula:
temp (degrees centigrade) = 5/9 × [temp (degrees Fahrenheit) – 32].
- **Body Mass Index (BMI)** – BMI is calculated using height (cm) and weight (kg) using the following formula:
BMI (kg/m²) = weight (kg)/[[height (cm)/100]²].
- **Change from baseline** – Change from baseline will be calculated as:
Change = post-baseline value – baseline value.
- **Percent change from baseline** – Percent change from baseline will be calculated as:
Percent change from baseline = (post-baseline value – baseline value)/baseline value × 100.

PPD

Horizon Therapeutics Ireland DAC
HZNP-KRY-407

Statistical Analysis Plan 20SEP2021

